
## 7.3 Phlebotomy Risks

Risks associated with blood draw include discomfort, bleeding, bruising, and in rare cases, fainting and infection.

#### **7.4 Breach of Confidentiality**

While there is a chance that there might be a breach of confidentiality (loss of privacy), all attempts will be made to ensure that this does not happen. To ensure the utmost protection of confidentiality all laboratory specimens, evaluation forms, reports, and other records that leave the site will be identified by coded number only. The link to the subject will be maintained in a locked cabinet in a locked room. All computer entry will be done with coded numbers only.

#### **7.5 Potential Benefits**

There are no direct benefits from this study for enrolled subjects. However, the results of the study might help increase our understanding of the pathogenesis of HIV disease.

### **8 RESEARCH USE OF STORED HUMAN SAMPLES, SPECIMENS, OR DATA**

**Intended Use:** Samples and data collected under this protocol may be used to study HIV infection, immune disorders, and interactions of HIV and host immune metabolic and genetic factors. Genetic testing will be performed.

**Storage:** Access to stored samples will be limited using either a locked room or a locked freezer or both. Samples and data will be stored using codes assigned by the investigators or their designees. Data will be kept in password-protected computers. Only investigators or their designees will have access to the samples and data.

**Tracking:** Stool specimens will be stored at the Uniformed Services University. All other study research-related samples will be sent to the NIH, stored, and tracked utilizing the Frederick National Laboratory for Cancer Research (formerly NCI-FCRF) Repository operated by Leidos Biomedical Research, Inc.

#### **8.1 Disposition at the Completion of the Protocol**

In the future, other investigators (both at NIH and outside) may wish to study these samples and/or data. In that case, IRB approval must be sought prior to any sharing of samples and/or data. Any clinical information shared about the sample would similarly require prior IRB approval. At the completion of the protocol (termination), samples and data will either be destroyed, or after IRB approval, transferred to another existing protocol.

#### **8.2 Reporting the Loss or Destruction of Samples/Specimens/Data to the IRB**

Any loss or unanticipated destruction of samples or data (for example, due to freezer malfunction) that meets the definition of Protocol Deviation and/or compromises the scientific integrity of the data collected for the study, will be reported to the NIAID IRB. Additionally, subjects may decide at any point not to have their samples stored. In this case, the principal investigator will destroy all known remaining samples and report what

was done to both the subject and to the IRB. This decision may not affect the subject's participation in this protocol or any other protocols at NIH.

## **9 REMUNERATION PLAN FOR SUBJECTS**

Subjects will be reimbursed for travel and study visits per local site standards (See Appendix C).

## **10 ASSESSMENT OF SAFETY**

### **10.1 Toxicity Scale**

The Division of AIDS Table for Grading the Severity of Adult and Pediatric Adverse Events, Version 1.0, 2004, (Clarification August, 2009) will be utilized for grading adverse events (see Appendix B).

### **10.2 Specification of Safety Parameters**

#### **Definitions**

##### **Adverse Event**

Any untoward or unfavorable medical occurrence in a human subject, including any abnormal symptom, sign, or disease, temporally associated with the subject's participation in the research, whether or not considered related to the research.

##### **Serious Adverse Event**

Serious adverse events (SAEs): Any adverse event that

- results in death;
- is life threatening (places the subject at immediate risk of death from the event as it occurred);
- results in inpatient or prolongation of existing hospitalization;
- results in a persistent or significant disability/incapacity
- results in congenital anomaly/birth defect; or
- based upon appropriate medical judgment may jeopardize the subject's health and may require medical or surgical intervention to prevent one of the other outcomes listed in this definition.

At the NIH site some individuals especially those travelling from some distance are admitted for convenience for study procedures. Elective admissions to the NIH will not be reported as SAEs.

##### **Expected Adverse Events**

Since rifaximin is an FDA-approved drug, adverse events described in the approved rifaximin package insert (label) will be considered to be expected.

**Unexpected Adverse Events** Those adverse events not described in the rifaximin

package insert, in the protocol, or in the informed consent document.

**Unanticipated Problem that is not an Adverse Event (UPnonAE)**

An unanticipated problem that does not fit the definition of an adverse event, but which may, in the opinion of the investigator, involve risk to the subject, affect others in the research study, or significantly impact the integrity of research data. These events may involve a greater risk of social or economic harm to subjects or others rather than physical/psychological harm. Such events would be considered a non-serious UP. Examples of a UPnonAE include a breach of confidentiality, accidental destruction of study records, and unaccounted-for study drug.

**Protocol Deviation**

Any change, divergence, or departure from the IRB-approved study procedures in a research protocol. Protocol deviations are designated as serious or non-serious and further characterized as

1. Those that occur because a member of the research team deviates from the protocol.
2. Those that are identified before they occur, but cannot be prevented.
3. Those that are discovered after they occur

**Serious Protocol Deviation**

A deviation that meets the definition of a Serious Adverse Event or compromises the safety, welfare or rights of subjects or others.

**Non-compliance**

The failure to comply with applicable NIH HRPP policies, IRB requirements, or regulatory requirements for the protection of human subjects. Non-compliance is further characterized as

1. Serious: Non-compliance that
  - a. Increases risks, or causes harm, to participants
  - b. Decreases potential benefits to participants
  - c. Compromises the integrity of the NIH-HRPP
  - d. Invalidates the study data
2. Continuing: Non-compliance that is recurring
3. Minor: Non-compliance that, is neither serious nor continuing.

**Unanticipated Problem (UP)**

An Unanticipated Problem is any event, incident, experience, or outcome that meets all three of the following criteria would be considered a serious UP:

1. unexpected in terms of nature, severity, or frequency in relation to
  - a. the research risks that are described in the IRB-approved research protocol and informed consent document; Investigator’s Brochure or other study documents; and
  - b. the characteristics of the subject population being studied; and

2. related or possibly related to participation in the research; and
3. suggests that the research places subjects or others at a greater risk of harm (including physical, psychological, economic, or social harm) than was previously known or recognized.

### **Intensity or Severity of Adverse Events**

Assignment of the grade of adverse events or side-effects of interventions is based on intensity of symptoms, degree of limitation of usual daily activities, or level of abnormality of objective clinical signs or laboratory parameters. All AEs that occur during the study will be assessed according to the DAIDS Toxicity Tables located in Appendix B or [http://rsc.tech-res.com/Document/safetyandpharmacovigilance/Table\\_for\\_Grading\\_Severity\\_of\\_Adult\\_Pediatric\\_Adverse\\_Events.pdf](http://rsc.tech-res.com/Document/safetyandpharmacovigilance/Table_for_Grading_Severity_of_Adult_Pediatric_Adverse_Events.pdf)

### **Reporting to IRBs**

For this study each institution will follow their institutions reporting requirements of their institution. Appendix D details the reporting requirements of all three institutions. Subjects enrolled in the NIAID will have their colonoscopy performed under protocol 95-I-0027, hence, colonoscopy related adverse effects observed among subjects co-enrolled in both protocols will also be reported. However, each event related to the colonoscopy (co-enrolled to 95-I-0027) procedure will be reported to the IRB under 95-I-0027. Grade 1 and 2 expected AEs will not be reported for this study. All SAE's definitely, possibly, or probably related to the drug and all unanticipated problems will be reported to all IRBs.

Each institution will follow their individual institutions reporting requirements. Appendix D details the reporting requirements of all other IRBs.

### **Relatedness of Adverse Event to an Intervention**

The study investigator's best assessment at the time of reporting of the causal relationship between an experimental intervention and an adverse event; the degree of certainty about causality is graded as follows:

#### **Definitely Related**

- reasonable temporal relationship
- follows a known response pattern
- clear evidence to suggest a causal relationship
- there is no alternative etiology

#### **Probably Related**

- reasonable temporal relationship
- follows a suspected response pattern (based on similar agents)
- no evidence of a more likely alternative etiology

#### **Possibly Related**

- reasonable temporal relationship

- little evidence for a more likely alternative etiology

**Unlikely Related**

- does not have a reasonable temporal relationship  
OR
- good evidence for a more likely alternative etiology

**Not Related**

- does not have a temporal relationship  
OR
- definitely due to an alternative etiology

**10.3 Recording/Documentation**

At each contact with the subject, information regarding adverse events will be elicited by appropriate questioning and examinations and will be immediately recorded on a source document. Source documents will include: progress notes, laboratory reports, consult notes, phone call summaries, survey tools and data collection tools. Source documents will be reviewed in a timely manner by the research team. All reportable adverse events that are identified will be recorded per local site standards [in CRIMSON at NIH, or on the appropriate case report form (CRF) at the University of Pittsburgh and WRNMMC]. The start date, the stop date, the severity of each reportable event, and the PI's judgment of the AEs relationship to the study agent/intervention will also be recorded [in CRIMSON, or on the appropriate CRF, or source document].

**10.4 Reporting Procedures**

Since this clinical trial is being conducted at 3 separate clinical sites, the local reporting requirements of all 3 clinical sites will be met. Adverse events will be reported per the individual institutions requirement detailed in Appendix D. The site Principal Investigator will be responsible for assuring all reporting requirements are fulfilled in a timely manner. These reporting requirements are detailed in Appendix D. [name] will provide oversight to ensure study progress and the timely communication of adverse effects to all 3 IRBs. To facilitate this process, AEs occurring at any of the sites will be reported by the study personnel to the site PIs and the lead PI (namely Drs. [name], [name], and [name]) and will be submitted on CRFs and via electronic mail. In addition AEs will be discussed at team calls that will occur twice a month and ad-hoc as needed. Specifically the following will be discussed: all unexpected adverse events, all grade 3 and 4 expected adverse events, and any other adverse events in the PI's opinion that may jeopardize the subject's health, confidentiality or well-being. Unanticipated problems involving breach of confidentiality/privacy or HIPAA violation which place subjects or others at a greater risk of harm (including physical, psychological, economical, or social harm) that was not previously known or recognized will be discussed. A standardized excel spread sheet will be used to capture all AEs, Appendix F. This excel spread sheet will created using the data from CRIMSON

## **10.5 Reporting of Pregnancy**

All unanticipated pregnancies will be reported to the IRB. All pregnant subjects will be followed on study until the completion of pregnancy.

## **10.6 Pausing and Halting Rules for the Protocol**

The study will be paused (no new enrollments and no further administration of agent by the investigators) if the study is deemed to pose a significant risk to subjects enrolled in the study. In general, we do not anticipate significant risks requiring pausing because the interventional agent is FDA-approved and will be used at approved doses. If we experience grade 3 or 4 unexpected adverse events in two subjects thought to be related to rifaximin, we will pause the study. In this case a report will be submitted to the IRBs and the study will be reviewed by the DSMB. After the DSMB review, the study may be resumed if so recommended by the DSMB, with the approval of the IRBs.

The IRB, the NIAID, or other government agencies, as part of their duties to ensure that research subjects are protected, may discontinue the study at any time. Subsequent review of serious, unexpected and related adverse events by the DSMB, ethics review committee or IRB, the sponsor(s), and other regulatory authorities may also result in suspension of further trial interventions/administration of study agent at a site. Regulatory authorities and the study sponsor(s) retain the authority to suspend additional enrollment and Study Agent(s)/Intervention(s) administration for the entire study as applicable.

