In general, the use of antibiotics has been associated with emergence of *Clostridium difficile* diarrhea. While no cases of *C. difficile* were reported in a study of IBS subjects randomized to receive a 2 week course of rifaximin, [92] three cases of *C.difficile* colitis were observed (2 in the rifaximin arm and 1 in the placebo arm) in the randomized placebo-controlled trial that examined the use of rifaximin in subjects with HE.[19] In this study, subjects who developed *C.difficile* while receiving rifaximin reported other concurrent risk factors including multiple recent hospitalizations, receipt of proton pump inhibitors, and other antibiotics[19]. Rates of *C.difficile* colitis in this study were similar between the rifaximin and placebo arm. While it is possible that rifaximin use resulted in *C. difficile* colitis in these two study participants, it is interesting to note that rifaximin has *in vitro* activity against *C. difficile*,[94] and has shown utility in refractory *C. difficile* infection in combination with vancomycin, and as sequential therapy [95-97].

Adverse effects are limited and mostly confined to the gastrointestinal tract. The following side effects have been observed in over 2% of subjects treated with rifaximin for travelers' diarrhea: flatulence, headache, abdominal pain, rectal tenesmus, defecation urgency, nausea, constipation, pyrexia, and vomiting. It is important to note that the dose and duration of rifaximin used for the treatment of travelers' diarrhea is lower and shorter than that being used in this study. Hypersensitivity to rifaximin has been rarely observed in post-marketing experience,[98] and is characterized by exfoliative dermatitis, rash, angioneurotic edema, urticaria, flushing; pruritus and anaphylaxis have been reported. Rifaximin is considered a pregnancy category C agent, and its excretion in breast milk is unknown.

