## **7 POTENTIAL RISKS AND BENEFITS**

### **7.1 Potential Risks Associated with Rifaximin**

Short term use of rifaximin is well-tolerated and frequencies of adverse events associated with this drug are similar to placebo. To date, there have been no randomized clinical trials in HIV-positive subjects. In several studies examining the effects of the drug as maintenance therapy in subjects diagnosed with decompensated liver disease and hepatic encephalopathy, as well as subjects diagnosed with irritable bowel syndrome, the emergence of treatment-emergent adverse effects (TEAEs) were similar in subjects randomized to placebo and rifaximin [19] [103]. The following adverse events have been reported in greater than 2% of subjects taking the 200 mg dose of rifaximin: flatulence, headache, abdominal pain (not otherwise specified), rectal tenesmus, defecation urgency, nausea, constipation, pyrexia, vomiting (not otherwise specified). The package insert accompanying this protocol provides information of side effects observed in less than 2% of subjects. The following events have been observed in the post-marketing experience: hypersensitivity reactions including exfoliative dermatitis, rash, angioneurotic edema, urticaria, flushing, and pruritus[98]. The 550 mg dose of rifaximin has been approved for use in patients with hepatic encephalopathy. At this dose in patients with hepatic encephalopathy [HE] the following events have been described in >5% of the patients (these include adverse events that may be attributable to the disease) peripheral edema, nausea, dizziness, fatigue, ascites, muscle spasms, pruritus, abdominal pain, abdominal distension, anemia, cough, depression, insomnia, nasopharyngitis, abdominal pain upper, arthralgia, back pain, constipation, dyspnea, pyrexia, rash. The 550 mg dose of rifaximin will be used for this study. [103]

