#### **Other Risks Associated With Rifaximin**

Similar to other antibiotics, rifaximin use has been associated with *C. difficile* infection. In studies where rifaximin has been studied as maintenance therapy the incidence of *C. difficile* infection in subjects receiving rifaximin were no greater than the placebo arm and were similar to the background rates in this population. Subjects will be followed closely for the development of diarrhea, fever, abdominal cramps, or bloody stools [19]. In general, use of antimicrobial therapy may be associated with the emergence of bacterial resistance. Studies have demonstrated emergence of resistance with rifaximin therapy [80]. The consequences of this event are unknown and subjects will be monitored closely for any bacterial infection during therapy. While all risks to the subjects cannot be anticipated, all reasonable attempts will be made to ensure subject safety. This will include the evaluations outlined in Table 1.

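### The two-subject pausing count in section 10.6 cannot register severe C. difficile infection or hypersensitivity; a fixed count that prompts a DSMB review would be a cheap improvement

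*Combined protocol and SAP*

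**What the plan says.** Section 10.6 gives two routes to a pause. One is a judgement that the study poses a significant risk to subjects. The other is the only count: "If we experience grade 3 or 4 unexpected adverse events in two subjects thought to be related to rifaximin, we will pause the study". After such a pause the DSMB reviews the study and may recommend resuming. The second paragraph of 10.6 adds that the IRB, NIAID or other agencies may discontinue the study at any time. It also lists "Subsequent review of serious, unexpected and related adverse events by the DSMB", among other bodies, as something that may lead to suspension.

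Section 10.2 supplies the definition of unexpected adverse events: "Those adverse events not described in the rifaximin" (the sentence continues) "package insert, in the protocol, or in the informed consent document". Expected events are those in the label. Neither definition mentions severity or frequency. A different term in 10.2, the unanticipated problem, does carry such a test: "unexpected in terms of nature, severity, or frequency in relation to" the documented research risks and the study population.

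The protocol describes the harms at issue. Section 7.1 lists "hypersensitivity reactions including exfoliative dermatitis, rash, angioneurotic edema, urticaria, flushing, and pruritus" from post-marketing experience. Under Other Risks it says "Similar to other antibiotics, rifaximin use has been associated with" C. difficile infection. Section 1.1, on hypersensitivity, adds that "pruritus and anaphylaxis have been reported".

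**The concern.** Known serious harms of an antibiotic are the events for which a safety rule is most likely to be needed, yet the one count in 10.6 is confined to surprises. The section supports its light rule by noting that the drug is FDA-approved and used at approved doses. Section 7.1, however, says there have been no randomized trials in HIV-positive subjects, and section 7.5 says participants have no direct benefit. If several subjects had related severe C. difficile infection or severe hypersensitivity, no number of cases would oblige anyone to convene the DSMB. Someone would have to recognise the cluster and choose to escalate it.

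**Working it through.** The plan states no operating characteristics for the pausing rule, so there is no figure of its own to reproduce. The check is a reading of definitions, followed by a calculation of what a count for the named harms would cost.

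**Step 1: does the count register these events?**

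- 10.6 requires an event that is grade 3 or 4, related and unexpected, in two subjects.
- 10.2 makes an event unexpected only if it is absent from the insert, the protocol and the consent. Description in any one of them is enough to make it expected.
- C. difficile infection is described in 1.1 and 7.1, exfoliative dermatitis and angioneurotic edema in 1.1 and 7.1, and anaphylaxis in 1.1.
- Contribution of related grade 3 or 4 cases to the count: 0, at any event rate. The package insert and consent form are not needed for this conclusion.

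**Step 2: where do such events go instead?**

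| Route | Section | Depends on expectedness? | Fixed number? |
|---|---|---|---|
| Pause for significant risk | 10.6 | No | No |
| Powers of IRB, NIAID, other agencies, sponsor, regulators | 10.6 | No | No |
| All SAEs and unanticipated problems to the DSMB; reviews as needed | 11.2 | SAEs: no | No |
| Related SAEs to all IRBs; to the NIAID IRB within 7 days | 10.2, Appendix D | No | No |
| Unanticipated problem for unexpected nature, severity or frequency | 10.2 | Yes, with the wider test | No |
| WRNMMC medical monitor, who receives all AEs and may stop the study | Appendix E | No | No |
| Subject-level stopping | 10.7 | No | One subject only |

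Grade is not itself a seriousness criterion in 10.2. A related grade 3 listed event that is neither an SAE nor an unanticipated problem therefore has no stated case-by-case route to the DSMB. It goes to the site and lead investigators and the team calls (10.4), the annual NIAID IRB summary (Appendix D) and scheduled DSMB reviews (11.2). Few of the named harms would fall in that group.

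**Step 3: how often would a two-subject count prompt a review?**

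Inputs: 44 subjects with one rifaximin course each (12.3), and a per-course risk p of a related grade 3 or greater case. The documents give no value for p, so it is assumed. The courses are treated as independent.

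P(at least 2) = 1 − (1−p)^n − n·p·(1−p)^(n−1)

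- n = 44, p = 0.5%: 1 − 0.802 − 0.177 = 0.021
- n = 44, p = 1%: 1 − 0.643 − 0.286 = 0.072 (from unrounded terms)

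Relatedness is the investigator's assessment when the event is reported (10.2), and the trial is double-blind, so placebo-phase events may also be judged related. If the same risk applied to all 88 courses, and every case were judged related:

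- n = 88, p = 0.5%: 0.072
- n = 88, p = 1%: 0.22

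The 88-course figures are slightly high, because two events in one subject would count once. Over 44 courses at larger assumed risks, the probability is 0.22 at 2%, 0.65 at 5% and 0.94 at 10%. The rule would be quiet if these harms are rare and would usually act if they were common. Replacement of withdrawn subjects (10.8) could raise the number of courses a little above 44.

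**The case against.** The strongest reply is that limiting an automatic pause to unexpected related events is a legitimate design choice, with known risks left to the DSMB and IRBs. The DSMB reviews the protocol before enrollment. Severe C. difficile colitis, anaphylaxis, angioedema and exfoliative dermatitis would commonly be SAEs under 10.2, which includes events that on medical judgement may need intervention to prevent a worse outcome. They would then reach the DSMB at the same time as the IRB. A cluster of unusual severity or frequency could itself be an unanticipated problem. The DSMB may already hold reviews as needed, so the added rule compels only something it can do anyway.

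Most of this stands, and it sets the size of the point. It does not remove it. None of these routes names a number of cases at which a review must happen, and each depends on someone judging that a pattern has emerged.

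Some stronger readings are tempting but unsupported:

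- *A cluster of these events could not pause the trial.* It could: the significant-risk clause and the powers in 10.6 have no expectedness condition. The sentence quoted from its second paragraph adds a route and does not limit the others.
- *Deaths escape, because 10.6 says grade 3 or 4 while 10.7 says grade 3 or greater.* Death is an SAE (10.2), goes to the NIAID IRB within 7 days (Appendix D) and is reported to the DSMB (11.2).
- *Subjects would keep taking dispensed capsules during a pause.* The natural reading of the pause in 10.6 is that dosing stops.
- *Rifaximin raises the risk of C. difficile infection.* Section 1.1 reports 2 cases on rifaximin and 1 on placebo in the encephalopathy trial, the rifaximin cases having other risk factors, and none in the irritable bowel trial. No increase is shown.

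**Conclusion.** The point holds as a cheap improvement. On the text, related grade 3 or 4 C. difficile infection and hypersensitivity contribute nothing to the only pausing count, because 10.2 treats any event described in the protocol as expected, whatever its severity or frequency. The consequence is modest: reporting and discretionary safeguards cover these events, and only a fixed number that requires DSMB review is absent.

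The 2% to 7% range rests on assumed per-course risks of 0.5% to 1% over 44 courses; it becomes 7% to 22% if placebo-phase events at the same risk are all judged related. These are chances of an extra review, not of the trial stopping, and they do not show how often a review would change a DSMB decision. Low risks are plausible: prior C. difficile colitis and chronic antibiotic use are exclusions, and section 1.1 calls hypersensitivity rare. Appendix D as available sets out the NIAID rules; the other two IRBs may add routes that cannot be checked here.

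**What to change.** Add one sentence to 10.6: *Related C. difficile infection or hypersensitivity of grade 3 or greater in two subjects, whether or not expected, prompts an ad hoc DSMB review.* It calls for a review and not an automatic halt, and the sponsor and DSMB may prefer another number.

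Optionally, align the 10.2 definition of unexpected adverse events with the three-part test already used for unanticipated problems, so that the word has one meaning. That alone would not be enough, since deciding that a severity or frequency is unexpected is itself a judgement.

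The cost is a wording change and an occasional extra DSMB review, at the frequencies given above. No new data are needed, because expected grade 3 and 4 events are already discussed on calls held twice a month (10.4). Aligning the definition might bring a few more low-grade events onto those calls.
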